The completely resected lesion should continue to be documented on the case report forms (CRFs) and assigned a default code of absent (for nontarget lesions) or a value of 0 mm for the longest diameter for the purpose of calculating the sum of the diameters (for target lesion), and determining the post intervention-therapy response. This will allow continued response determination from screening.

If the resected lesion contained no tumor under pathology evaluation, subsequent tumor assessments post-procedure may be used for tumor burden calculations and/or determination of response. If the resected lesion contained tumor or pathology results were unknown, the recorded tumor assessments post-procedure may be used for tumor burden calculations, but determination of response will be considered unevaluable (UE) for response except in the case of PD. If the new tumor burden post-procedure is lower than the nadir before the procedure, then the new nadir will be set to the post-procedure tumor burden. Otherwise, the previous pre-procedure nadir will be retained as the nadir. Subsequent assessments for PD will be determined from the nadir.

Guidance on quantitative/qualitative reporting of fully resected lymph nodes is below (see [Table 21](#)).

If new radiographic imaging findings develop at the surgical/treatment site that were not present on the immediate post intervention-therapy imaging assessments and are indicative of tumor recurrence, the tumor will be considered a new lesion, and measured accordingly, with the response assessed as PD if increase in tumor burden $\geq 20\%$ and at least 5 mm absolute increase relative to nadir compared with the first post intervention-therapy nadir at two time points at least 4 weeks (28 days) apart.

Table 21. Quantitative/Qualitative Reporting of Fully Resected Lymph Nodes

Lymph Node Type/Presence	Contained Cancer Under Pathology Evaluation?	Quantitative/qualitative Reporting
Target lymph node previously present	Yes/Unknown	If measurement available: Actual short axis
		If measurement not available: 10 mm short axis
	No	If measurement available: Actual short axis
		If measurement not available: 9 mm short axis
Non-target lymph node previously present	Yes/Unknown	Present
	No	Absent
Lymph node not previously present	Yes/Unknown	If measurement available and short axis < 15 mm: New non-measurable lymph node ^a
		If measurement available and short axis ≥ 15 mm: please enter actual measurements (do not default to 10 mm) ^a

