## Best overall response (BOR) per Modified irRC-RECIST

Best overall response (BOR) of complete response (CR), partial response (PR), stable disease (SD), progressive disease (PD) or un-evaluable (UE) will be derived based on investigator assessment using modified irRC-RECIST as defined in protocol Appendix D.

Overall visit response assessments occurring after the start of the first subsequent anticancer therapy **will not be included. With the exception of a PD observation, the overall visit response** occurring on or after complete or partial removal/reduction of any target lesion which contained cancer on pathology evaluation or pathology results were unknown, will not be included. Consecutive confirmation of CR, PR, and PD is required where the second overall response must be at least 28 days from the first, the only exception being when the investigator reports that an initial PD cannot be confirmed due to rapid clinical deterioration. The following will be considered a confirmed PR: CR followed by PR or PR followed by CR.

BOR is defined as the best visit response in the following order: CR, PR, SD, PD, or UE (see [Table 1](#)). BOR is defined as SD if the best overall visit response is an unconfirmed CR or PR, and UE if it is either SD earlier than 77 days after first dose date or an unconfirmed PD when confirmation of PD is required (ie, initial PD without rapid clinical deterioration).

Table 1. Matrix of Determining BOR per Modified irRC-RECIST

Visit Overall Response Sequence	Examples	Best Overall Response	Confirmation specifications
*, CR, CR,*	PR, CR, CR CR, CR, PD	CR	The confirmatory CR must be at least 4 weeks (28 days) later; a subsequent CR within 28 days will not be valid for

			confirmation and will be ignored; the CR will also not be confirmed if there is a subsequent PR/SD/PD at any time prior to the next CR.
* , PR, PR, *  * , PR, CR/PR, non-CR, *  * ,CR, PR,*	PR, PR, PD PR, CR, PD  CR, PR, PD	PR	Criteria for BOR=CR not met. The confirmatory PR/CR must be no less than 4 weeks (28 days) later; a subsequent PR/CR within 28 days will not be valid for confirmation and will be ignored; the PR will also not be confirmed if there is a subsequent SD/PD at any time prior to the next PR/CR.
* , SD, *  * ,CR, non-PR/CR, *  * ,PR, non-PR/CR, *	CR PD, CR PR PD, PR, SD SD PD,SD,PD	SD	Criteria for BOR=CR or PR not met. SD must be $\geq 77$ days from the date of first dose; however, this is not required for an unconfirmed CR/PR.

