### **Duration of Response (DOR)**

Duration of response is defined as the time from the date of an initial response that is subsequently confirmed to the earlier of PD (see definition of BOR per modified irRC-RECIST) or death. Subjects who have not ended their response at the time of analysis will be censored at the last evaluable tumor assessment before start of the first subsequent anticancer therapy.

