### **Durable Response Rate (DRR)**

Durable response rate is defined as the percent of subjects with a CR or PR per modified irRC-RECIST with a DOR  $\geq$  6 months. One month will be calculated based on 365.25 days per year.

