### **Evaluable tumor assessment**

An overall visit response other than unevaluable (UE) or not done (ND).

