### **Progression-free survival (PFS)**

PFS is defined as the interval from first dose date to the earlier event of confirmed PD or death from any cause. Subjects without an event will be censored at the latter of their last evaluable tumor assessment if available; otherwise will be censored on Study Day 1.

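### After resection of a tumor-containing lesion only PD visits stay evaluable, so censoring of PFS and DOR depends on the outcome

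*Protocol*

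**What the plan says.** - Protocol Appendix D, on complete removal of a lesion: if the specimen contained tumor or pathology is unknown, later measurements may enter the tumor burden, but "determination of response will be considered unevaluable (UE) for response except in the case of PD". The part on partial removal repeats this. PD continues to be judged from the nadir, which is reset if the post-procedure burden is lower.
- SAP Section 5, best overall response, has a matching rule: "With the exception of a PD observation, the overall visit response" is left out when "occurring on or after complete or partial removal/reduction of any target lesion which contained cancer on pathology evaluation", or when pathology is unknown.
- SAP Section 5, evaluable tumor assessment: "An overall visit response other than unevaluable (UE) or not done (ND".
- SAP Section 5, PFS: time runs from first dose to confirmed PD or death, with no stop at resection. For everyone else the rule is that "Subjects without an event will be censored at the latter of their last evaluable tumor assessment if available", failing which the date is Study Day 1.
- SAP Section 5, DOR: "Subjects who have not ended their response at the time of analysis will be censored at the last evaluable tumor assessment" before subsequent anticancer therapy.
- SAP Section 5, DRR: "percent of subjects with a CR or PR per modified irRC-RECIST with a DOR" of at least 6 months. Nothing is said about a DOR censored before 6 months.
- Protocol Section 6.6 allows resection of lesions that become resectable on treatment. It keeps surgical CR or PR out of ORR and BOR and is silent on PFS, DOR and DRR.
- SAP Table 9-2 lists no sensitivity analysis for these endpoints.

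**The concern.** Treating post-surgical visits as unevaluable is sensible for best response, because surgery has altered the tumor burden. Carried into PFS and DOR through the definition of an evaluable assessment, the same label makes follow-up after surgery count only for subjects who go on to have an event. That is informative censoring. It falls on subjects who are probably doing well, since resection is foreseen for those whose disease has shrunk.

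No other rule removes it. The PFS definition has no stop at resection. DOR stops at subsequent anticancer therapy, but the SAP lists lesion removal separately from such therapy when it defines lesion-level response and maximum tumor burden decrease. Those two measures are censored at removal whatever follows, so the SAP has a symmetric rule elsewhere but not for PFS or DOR.

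At stake are the Kaplan-Meier landmarks and quartiles for PFS and DOR, and the crude DRR, in arms small enough for one or two subjects to show.

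**Working it through.** The plan states no figure for PFS, DOR or DRR, so there is none to reproduce on this point. The two-stage ORR figures do reproduce by exact binomial calculation (significance level 1.3%, power 88.4%, early stopping 73.6% and 4.6%), and the rule does not touch them.

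**Tracing two responders.** Scans are at week 10 and then every 9 weeks (Protocol Section 7.2.2), that is days 64, 127, 190 and so on. Both have PR on day 64, confirmed on day 127, and a tumor-containing lesion resected on day 150.
- Subject A has no PD through month 24. All visits after day 150 are UE, so DOR is censored at day 127: (127 − 64)/30.4375 = 2.1 months. Under a crude DRR this is not durable.
- Subject B has PD on day 568, later confirmed: (568 − 64)/30.4375 = 16.6 months, an event, and durable.

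Had the last pre-surgery scan come 6 months or more after response, both would be durable.

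**PFS illustration.** Assumptions, none from the documents except the scan schedule: exponential PFS with median 12 months, 24 months of follow-up, resection at month 6, hazard unchanged by surgery. The share progression-free at month 6 is 0.5^(6/12) = 70.7%. Resecting 30% of these gives 0.30 × 70.7% = 21% of all subjects; resecting 15% gives 11%. Simulated Kaplan-Meier PFS at 18 months:

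| Share resected | Rule as written | All visits kept | Difference | All resected censored before surgery |
|---|---|---|---|---|
| 21% | 33.7% | 38.3% | 4.6 points | 36.7% |
| 11% | 36.4% | 38.5% | 2.1 points | 37.9% |

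Repeat runs vary by a few tenths of a point. Symmetric censoring recovers most of the gap.

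**DOR and DRR illustration.** Assumptions: exponential DOR with median 6, 12 or 24 months; resection scheduled for 10%, 20% or 40% of responders, 1 to 6 months after response; 12 to 24 months of follow-up. In all nine scenarios Kaplan-Meier DOR was lower under the written rule than with all visits kept, by 0.3 to 1.6 points at 6 months and 0.9 to 6.7 points at 12 months. For median 12 months and 20% scheduled:

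| Handling | 12-month DOR | Crude DRR among responders |
|---|---|---|
| Rule as written | 0.521 | 0.710 |
| All visits kept | 0.551 | 0.787 |
| All resected censored before surgery | 0.544 | 0.633 |

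Under the written rule 85% to 91% of resected later progressors counted as durable, and none of the resected non-progressors did.

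**The case against.** The strongest reply is that the unevaluable status is less settled than the literal chain suggests. Appendix D says unevaluable for response, which could leave the visit usable for progression. Its complete-removal text also says that coding a removed lesion as 0 mm allows response determination to continue, and its partial-removal text asks for response to be determined where residual tumor can be identified. Section 6.6 assigns PR dated at surgery in some cases. The SAP exclusion sits in the BOR definition and covers target lesions only. So a reader might infer that every post-surgical visit is uniformly unevaluable, and the documents do not support that: they conflict. What survives is that the SAP defines evaluability by the overall visit response, with no separate progression status. A programmer following that text produces the asymmetry.

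Three further limits stand. Resections may be rare: candidates for curative-intent surgery are excluded, and tumor-free specimens are exempt from the rule. An arm with no such resection is unaffected. A post-surgical PD that is never confirmed is itself evaluable, so that subject is censored at that visit and not before surgery. Finally, PFS, DOR and DRR are secondary, and Protocol Section 10.4 confines formal analysis to the Part 2 primary endpoints.

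**Conclusion.** The point holds as a defect in the written rules. Subjects resected with tumor present or pathology unknown are censored before surgery if they remain event-free, and followed to the event if they do not. The direction is downward for Kaplan-Meier PFS and DOR, relative to handling both kinds of subject alike. The size rests on an assumed resection rate: about 4.5 points at 18 months with 21% resected, about 2 points with 11%.

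Two stronger readings are not supported. First, these differences are not bias against the true survival curve. With median 12 months, true 18-month PFS is 0.5^1.5 = 35.4%. The 38.3% with all visits kept is higher because progression is only seen at scans; the last scan before month 18 is day 505, and 0.5^(16.59/12) = 38.4%. Second, DRR does not invert for every resected responder. It does so only when the last pre-surgery scan is under 6 months after response, and only if a DOR censored before 6 months is read as not durable, which the SAP leaves open.

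ORR, OS and the two-stage test are unaffected. With 53 Part 2 subjects over six arms, about 9 per arm, one subject moves an arm's crude DRR by about 11 points (1/9). The rule should be corrected, but it does not threaten the primary analysis.

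**What to change.** In SAP Section 5, state one symmetric post-resection rule for PFS, DOR and DRR. Either of two would do:
- treat non-PD visits after resection, judged against the applicable nadir, as evaluable for progression, while keeping them unevaluable for BOR and ORR; or
- censor every resected subject at the last pre-surgery assessment, whether or not PD or death follows.

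Run the other as a sensitivity analysis. Report the trade-off: the first credits time after surgical removal of tumor to DOR and DRR, and the second lowers crude DRR further. State how DRR handles a DOR censored before 6 months, for example by a 6-month Kaplan-Meier estimate among responders. Reconcile Protocol Section 6.6, both removal parts of Appendix D and the SAP BOR definition on response status after resection, and on whether the rule covers non-target as well as target lesions.

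The cost is wording and one derived flag. Imaging is already scheduled until confirmed PD, so no new data are needed.

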Appendix E. Drug-induced Liver Injury Reporting and Additional Assessment Reporting

To facilitate appropriate monitoring for signals of drug induced liver injury (DILI), cases of concurrent aspartate aminotransferase (AST) or alanine aminotransferase (ALT) and total bilirubin (TBL) and/or international normalization ratio (INR) elevation according to the criteria specified in Section 6.4, require the following:

- The event is to be reported to Amgen as a serious adverse event within 24 hours of discovery or notification of the event (ie, before additional etiologic investigations have been concluded)
- The appropriate CRF (eg, events CRF) that captures information necessary to facilitate the evaluation of treatment-emergent liver abnormalities is to be completed and sent to Amgen

Other events of hepatotoxicity and potential DILI are to be reported as serious adverse events if they meet the criteria for serious adverse events defined in Section 9.1.2.

Additional Clinical Assessments and Observation

All subjects in whom investigational product is withheld (either permanently or conditionally) due to potential DILI as specified in Section 6.4 are to undergo a period of “close observation” until abnormalities return to normal or to the subject’s baseline levels. Assessments that are to be performed during this period include:

- Repeat AST, ALT, ALP, bilirubin (total and direct), and INR within 24 hours
- In cases of TBL > 2x upper limit of normal (ULN) or INR > 1.5, retesting of liver tests, bilirubin (total and direct), and INR is to be performed every 24 hours until laboratory abnormalities improve

Testing frequency of the above laboratory tests may decrease if the abnormalities stabilize or the investigational product(s) or protocol-required therapies has/have been discontinued AND the subject is asymptomatic

- Initiate investigation of alternative causes for elevated AST or ALT and/or elevated TBL:

Obtain complete blood count with differential to assess for eosinophilia

Obtain serum total immunoglobulin G (IgG), anti-nuclear antibody, anti-smooth muscle antibody, and liver kidney microsomal antibody 1 to assess for autoimmune hepatitis

Obtain serum acetaminophen (paracetamol) levels

Obtain a more detailed history of:

Prior and/or concurrent diseases or illness

Exposure to environmental and/or industrial chemical agents

Symptoms (if applicable) including right upper quadrant pain, hypersensitivity type reactions, fatigue, nausea, vomiting and fever

Prior and/or concurrent use of alcohol, recreational drugs and special diets

Concomitant use of medications (including non-prescription medicines and herbal and dietary supplements), plants, and mushrooms

Obtain viral serologies

Obtain creatinine phosphokinase, haptoglobin, lactate dehydrogenase (LDH), and peripheral blood smear

Perform appropriate liver imaging if clinically indicated

- Obtain appropriate blood sampling for pharmacokinetic analysis if this has not already been collected
- Obtain hepatology consult (liver biopsy may be considered in consultation with an hepatologist)
- Follow the subject and the laboratory tests (ALT, AST, TBL, INR) until all laboratory abnormalities return to baseline or normal. The “close observation period” is to continue for a minimum of 4 weeks after discontinuation of investigational product.

The potential DILI event and additional information such as medical history, concomitant medications and laboratory results must be captured in corresponding CRFs.

Appendix F. Child-Pugh Score

Measure	1 point	2 points	3 points
Total bilirubin, $\mu\text{mol/l}$ (mg/dl)	< 34 (< 2)	34-50 (2-3)	> 50 (> 3)
Serum albumin, g/dl	> 3.5	2.8-3.5	< 2.8
INR/PT	< 1.7/4.0	1.7-2.3/4.0-6.0	> 2.3/6.0
Ascites	None	Mild	Moderate to Severe
Hepatic encephalopathy	None	Grade 1 to 2 (or suppressed with medication)	Grade 3 to 4 (or refractory)

Points	Class
5 to 6	A
7 to 9	B
10 to 15	C

References:

Appendix G. Eastern Cooperative Oncology Group Performance Status Scale

Grade	Description
0	Fully active, able to carry on all predisease performance without restriction.
1	Restricted in physically strenuous activity but ambulatory and able to carry out work of a light or sedentary nature, ie, light housework or office work.
2	Ambulatory and capable of all self-care but unable to carry out any work activities. Up and about > 50% of waking hours.
3	Capable of only limited self-care, confined to a bed or chair > 50% of waking hours.
4	Completely disabled. Cannot carry on any self-care. Totally confined to bed or chair.
5	Dead

Appendix H. Contraceptive Guidance and Collection of Pregnancy and Lactation Information For Talimogene Laherparepvec

Study-specific contraception requirements for female of childbearing potential are outlined in Section 4.1.2.

Female subjects of childbearing potential must receive pregnancy prevention counseling and be advised of the risk to the fetus if they become pregnant during treatment and after the last dose of protocol-required therapies.

Additional medications given during the study may alter the contraceptive requirements. These additional medications may require female subjects to use highly effective methods of contraception and for an increased length of time. In addition, male subjects may also be required to use contraception. The investigator must discuss these contraceptive changes with the subject.

Definition of Females of Childbearing Potential

A female is considered fertile following menarche and until becoming postmenopausal unless permanently sterile. Permanent sterilization methods include hysterectomy, bilateral salpingectomy, and bilateral oophorectomy.

Females in the following categories are not considered female of childbearing potential:

Premenopausal female with 1 of the following:

- Documented hysterectomy;
- Documented bilateral salpingectomy; or
- Documented bilateral oophorectomy.

Note: Site personnel documentation from the following sources is acceptable:

- 1) review of subject's medical records; 2) subject's medical examination; or
- 3) subject's medical history interview.

Premenarchal female

Postmenopausal female

- A postmenopausal state is defined as no menses for 12 months without an alternative medical cause. A high follicle stimulating hormone (FSH) level in the postmenopausal range may be used to confirm a postmenopausal state in women not using hormonal contraception or hormonal replacement therapy (HRT). However, in the absence of 12 months of amenorrhea, a single FSH measurement is insufficient.
- Females on HRT and whose menopausal status is in doubt will be required to use 1 of the non-hormonal highly effective contraception methods if they wish to continue their HRT during the study. Otherwise, they must discontinue HRT to allow confirmation of postmenopausal status before study enrollment.

Acceptable Methods of Effective Contraception

- Combined (estrogen and progestogen containing) or progestogen-only hormonal methods given via oral, intravaginal, transdermal, injectable, or implantable route)
- Intrauterine device (IUD)
- Intrauterine hormonal-releasing system (IUS)
- Bilateral tubal ligation/occlusion
- Vasectomized partner (provided that partner is the sole sexual partner of the female subject of childbearing potential and that the vasectomized partner has received medical assessment of the surgical success)
- Sexual abstinence (defined as refraining from heterosexual intercourse during the entire period of risk associated with the study treatments; the reliability of sexual abstinence must be evaluated in relation to the duration of the trial and the preferred and usual lifestyle of the subject)
- Double barrier method: the male uses a condom and the female may choose either a cap, diaphragm, or sponge with spermicide (a female condom is not an option due to the risk of tearing when both partners use a condom)

Unacceptable Methods of Birth Control for Female Subjects

Birth control methods that are considered unacceptable in clinical trials include:

- Periodic abstinence (calendar, symptothermal, postovulation methods)
- Withdrawal (coitus interruptus)
- Spermicides only
- Lactational amenorrhoea method

Appendix I. Contraceptive Guidance and Collection of Pregnancy and Lactation Information For Pembrolizumab

Pembrolizumab may have adverse effects on a fetus in utero. Furthermore, it is not known if pembrolizumab has transient adverse effects on the composition of sperm.

Subjects should be informed that taking pembrolizumab may involve unknown risks to the fetus (unborn baby) if pregnancy were to occur during the study. In order to participate in the study, men and women of reproductive potential must adhere to the contraception requirements (See Section 4.1.2, exclusion criteria 224, 225, and 226) from the day of pembrolizumab initiation (or 14 days prior to the initiation of pembrolizumab for oral contraception) throughout the study period up to 4 months (120 days) after the last dose of pembrolizumab. If there is any question that a subject of reproductive potential will not reliably comply with the requirements for contraception, that subject should not be enrolled into the study.

Use of Pembrolizumab in Pregnancy

If a subject inadvertently becomes pregnant while on treatment with systemic pembrolizumab, the subject will immediately be removed from the study. The outcome of the pregnancy will be reported to the sponsor and followed as described in Section 9.3 (Pregnancy and Lactation Reporting). If a male subject impregnates his female partner, the investigator must be informed immediately and the pregnancy reported to the sponsor and followed as described in Section 9.3 (Pregnancy and Lactation Reporting).

Use of Pembrolizumab in Nursing Women

It is unknown whether pembrolizumab is excreted in human milk. Since many drugs are excreted in human milk, and because of the potential for serious adverse reactions in the nursing infant, female subjects who are breast-feeding are not eligible for enrollment in this study.

Amendment 6

Protocol Title: A Phase 1b/2, Multicenter, Open-label, Basket Trial to Evaluate the Safety of Talimogene Laherparepvec Injected into Liver Tumors Alone and in Combination With Systemic Pembrolizumab in Phase 1b and to Evaluate the Efficacy and Safety of Intratumoral Talimogene Laherparepvec in Combination With Systemic Pembrolizumab to Treat Subjects With Advanced Solid Tumors in Phase 2 (MASTERKEY-318)

Amgen Protocol Number (Talimogene Laherparepvec 20140318)

EudraCT number: 2014-005386-67

NCT number: NCT02509507

Amendment Date: 26 October 2021

Rationale:

This protocol is being amended to stop study-related hepatic biopsies and hepatic injections of talimogene laherparepvec based on the overall safety assessment of the hepatic hemorrhage signal following two serious adverse events of hepatic haemorrhage that resulted in death in the study. While the full safety assessment results did not suggest an increased risk of hepatic haemorrhage with talimogene laherparepvec as a medication, there is a potential risk of hepatic haemorrhage with the transcutaneous intrahepatic route of administration of talimogene laherparepvec and hepatic biopsies. As a result, the protocol is amended to remove these procedures from study conduct. Additionally, the final enrollment numbers have been updated in the protocol as enrollment has stopped for this study.

Amendment 5

Protocol Title: A Phase 1b/2, Multicenter, Open-label, Basket Trial to Evaluate the Safety of Talimogene Laherparepvec Injected into Liver Tumors Alone and in Combination With Systemic Pembrolizumab in Phase 1b and to Evaluate the Efficacy and Safety of Intratumoral Talimogene Laherparepvec in Combination With Systemic Pembrolizumab to Treat Subjects With Advanced Solid Tumors in Phase 2 (MASTERKEY 318)

Amgen Protocol Number 20140318

EudraCT number: 2014-005386-67

NCT number: NCT02509507

Amendment Date: 02 July 2021

Rationale:

This protocol amendment dated 02 July 2021 is being amended to:

- fix the minor discrepancies and inconsistencies within the protocol
 - removed 'Swab of Injection Site Surfaces and Occlusive Dressings' at Week 10 from the table 12 to maintain consistency with footnotes
 - corrected number of days (missing in brackets) in footnote 't' of table 13 for the samples collected post 14 days after talimogene laherparepvec administration for all subjects at week 1 and 4
 - updated time points for specialized/central laboratory tests and tumor biopsy procedures in the section 7.2.2 to maintain consistency with footnotes of table 13
- clarified medical monitor approval requirements for continuing talimogene in Part 1 and Part 2 (section 3.1.3)
- updated exclusion criteria 207 to separate pneumonitis into standalone criteria 238
- removed the exclusion of prior checkpoint inhibitors for basal cell carcinoma (BCC) patients to reflect the approval of cemiplimab in this population
- updated Dose Modification and Toxicity Management Guidelines for Immune-related Adverse Events Associated With Pembrolizumab
- updated an exception considered to continue treatment beyond progression (Section 6.6)
- updated the requirement to report fatal disease related events (DREs) as serious adverse events (SAEs)
- clarified the interim safety analysis language in Part 2 (Section 10.3.1.2)

- updates SAE reporting forms
- updated pregnancy and lactation notification forms
- clarified primary and final analyses clinical study report (CSR) plans
- aligned the protocol with current Amgen protocol template and safety reporting language
- typographical, formatting, and editorial changes were done throughout the protocol

Amendment 4

Protocol Title: A Phase 1b/2, Multicenter, Open-label, Basket Trial to Evaluate the Safety of Talimogene Laherparepvec Injected into Liver Tumors Alone and in Combination With Systemic Pembrolizumab in Phase 1b and to Evaluate the Efficacy and Safety of Intratumoral Talimogene Laherparepvec in Combination With Systemic Pembrolizumab to Treat Subjects With Advanced Solid Tumors in Phase 2 (MASTERKEY-318)

Amgen Protocol Number 20140318

EudraCT number: 2014-005386-67

NCT number: NCT02509507

Amendment Date: 30 June 2020

Rationale:

This protocol is being amended to:

- Remove the 6 hour observation period and associated assessments for Part 2 subjects not receiving intrahepatic injections
- Only include Part 2 enrolled subjects as part of the efficacy futility analyses
- Combine study Arms VI and VII
- Make updates to collection time points of cytokines and quantitative polymerase chain reaction (qPCR)
- Decrease sample size from 244 to 206
- Clarify inclusion criterion for triple negative breast cancer subjects (inclusion criterion 114)
- Update administrative edits

Amendment 3

Protocol Title: A Phase 1b/2, Multicenter, Open-label, Basket Trial to Evaluate the Safety of Talimogene Laherparepvec Injected into Liver Tumors Alone and in Combination With Systemic Pembrolizumab in Phase 1b and to Evaluate the Efficacy and Safety of Intratumoral Talimogene Laherparepvec in Combination With Systemic Pembrolizumab to Treat Subjects With Advanced Solid Tumors in Phase 2 (MASTERKEY-318)

Amgen Protocol Number 20140318

EudraCT number: 2014-005386-67

NCT number: NCT02509507

Amendment Date: 21 October 2019

Rationale:

- This protocol is being amended to:
 - Update study title to reflect phase and type of study, combination therapy, and to indicate primary purpose of Phases 1b and 2
 - Allow intratumoral injection of talimogene laherparepvec into cutaneous, subcutaneous, and liver lesions and involved lymph nodes in Part 2 of the study, as safety of intrahepatic injection of talimogene laherparepvec in combination with systemic pembrolizumab will be established in Part 1. Intrahepatic injection is not required in Part 2, but it is allowed if there are injectable liver lesions
 - Clarify that liver injection is not a requirement or priority in Part 2
 - Expand allowable injectable disease to include subcutaneous and cutaneous tumor lesions and involved lymph nodes
 - Change the tumor types in Part 2 to the following non-HCC tumor types to reflect the expanded allowable injection sites: hormone receptor positive breast adenocarcinoma [BC], triple negative breast cancer [TNBC], colorectal adenocarcinoma [CRC], cutaneous squamous cell carcinoma (CSCC), basal cell carcinoma (BCC)
 - Create additional BC cohort to include separate cohorts for triple negative breast cancer (TNBC) and hormone receptor positive subjects
 - Create additional hepatocellular carcinoma (HCC) cohort to include separate cohorts for HCC subjects with and without viral hepatitis
 - Allow for well controlled viral hepatitis and allow antiviral therapy for hepatitis in new cohort 6B for HCC in Part 1 and Arm VI in Part 2 of the study
 - Change the sample size in Part 1 and Part 2 to reflect the number of cohorts/arms now under study
 - Update the study schema to reflect new cohort in Part 1 and new tumor types in Part 2
 - Update the eligibility criteria based on new cohorts and revised tumor types

Approved

- Shorten 23 hour observation window to 6 hours in Part 2, after review of safety data from monotherapy and combination cohorts enrolled to date in Part 1
- Add collection of Patch 1 (PTCH) mutation status in BCC cohort if available
- Add collection of BRCA1 and 2 mutation status in BC cohort if available
- Add optional liver ultrasound to schedule of assessments for monotherapy and combination cohorts enrolled to date in Part 1 and combination cohorts Part 2.
- Remove 24 hour and 48 hour timepoints in Week 1 and Week 4 from Part 2 schedule of assessments, after review of available data from Part 1
- Remove assessments for anti-pembrolizumab antibodies, and pembrolizumab pharmacokinetics (PK) in Part 2
- Remove blood, urine, and swab collection at 24, and 48 hours in Part 2, after review of available data from Part 1
- Allow continuation of talimogene laherparepvec after cycle 12 in Part 2 if in the opinion of the investigator, the subject is deriving clinical benefit from the study regimen, the subject is still receiving pembrolizumab, and the investigator obtains approval from the sponsor medical monitor
- Clarify that subjects can receive a maximum of 12 cycles of talimogene laherparepvec in Part 1 and 35 cycles in Part 2
- Allow resumption of talimogene laherparepvec at progression if previously discontinued
- Allow up to 8 mL of talimogene laherparepvec to be used in Part 2 if 8 mL is shown safe in either Group A or B in Part 1
- Add clinical tumor assessments in Part 2
- Create a separate schedule of assessment table for Part 2 to reflect the changes to cohort, tumor types, and time points
- Revise the list of laboratory analytes to align with new tumor types
- Add language regarding events of clinical interest specifically for Group B HCC subjects
- Add disease related events (DRE) language that instructs sites to transmit serious DREs in the same manner that they transmit serious adverse events and with the same timeline expectations
- Remove language on self-evident corrections from the protocol to be consistent with current regulations
- Update HCC data in the Background and Rationale section to reflect new available clinical data since the last amendment
- Update CTCAE version to 4.03
- Update references to reflect added information in the Background and Rationale section
- Make editorial and administrative changes for grammatical reasons as well as for internal consistency within the protocol

Approved

Amendment 2

Protocol Title: A Phase 1b/2, Multicenter, Open-label Trial to Evaluate the Safety of Talimogene Laherparepvec Injected Into Liver Tumors Alone and in Combination With Systemic Pembrolizumab (MASTERKEY-318)

Amgen Protocol Number Talimogene Laherparepvec 20140318

EudraCT number 2014-005386-67

NCT number NCT02509507

Amendment 2 Date: 18 October 2017

Rationale:

This amendment was revised to:

- Add a collaborator drug, pembrolizumab, from Merck. This resulted in:
 - Adding combination cohorts (talimogene laherparepvec and pembrolizumab) in Part 1 of the study
 - The opening on Group B will now be independent of Group A safety results
 - Phase of study changed to 1b/2
 - Changing Part 2 of the study to include combination cohorts only
 - Pembrolizumab-specific requirements added to the protocol
- Align with more recent protocol template text:
 - Section 9 (Safety Data Collection, Recording, and Reporting)
 - Updated the pregnancy and lactation reporting forms
 - Added contraception, pregnancy, and lactation information to Appendix H and Appendix I
 - Section 12.6 (Publication Policy)
- Editorial changes (ie, typographic, grammatical, and formatting errors) and abbreviation corrections were made throughout the protocol in accordance with Amgen Inc. Style Guide.

Approved

Amendment 1

Protocol Title: A Phase 1, Multicenter, Open-label Trial to Evaluate the Safety of Talimogene Laherparepvec Injected into Liver Tumors

Amgen Protocol Number TVEC 20140318

EudraCT number 2014-005386-67

Amendment Date: 26 April 2016

Rationale:

The previous version of the protocol considered a grade 3 or higher non-hematologic laboratory value that persisted for > 1 week as meeting the criteria for a DLT, even if the abnormal laboratory value did not result in a medical intervention or hospitalization. This criterion could result in dose limiting toxicities (DLTs) being determined for abnormal laboratory values that were not clinically important. To date, 1 subject has had a grade 3 or higher gamma-glutamyl transferase (GGT) elevation that persisted for over 1 week, which was considered related to talimogene laherparepvec, and was subsequently defined as a DLT under the original protocol. The subject was asymptomatic, and the GGT elevation was considered to not be of any clinical significance. In order to prevent abnormal laboratory values that are not clinically significant from being classified as DLTs, the Dose Level Review Team (DLRT) decided that the protocol should be amended. This modification will also be consistent with the protocol language in [Section 9.2.2](#), where abnormal laboratory findings without clinical significance (based on investigator's judgement) are not to be recorded as adverse events.

The following key changes have been incorporated into protocol amendment 1:

- The criteria for grade 3 or higher non-hematologic laboratory values that define DLT have been changed so that those that persist for > 1 week which are deemed not clinically important by both the investigator and sponsor do not trigger a DLT. Any grade 3 or higher non-hematologic laboratory value will still be considered a DLT if medical intervention is required or if it leads to hospitalization.
- Treatment can continue for grade 3 or higher non-hematologic laboratory values that persist for > 1 week and are deemed not clinically important by both the investigator and sponsor so that subjects can continue study treatment in spite of persistently elevated non-hematologic laboratory values with no clinical significance and long half-lives such as GGT.
- Added hepatitis D viral RNA as another acceptable method of testing as some institutions do not use hepatitis D serology testing.

- The irRC-RECIST criteria definition has been edited to make it more consistent with the conventional RECIST criteria and irRC simulating RECIST as described by Nishino et al.
- Clarified certain laboratory tests and timing of study procedures.
- Other minor changes include:
 - Administration and editorial corrections
 - Updating adverse event and disease related event language to clarify definitions and reporting periods
 - Specifying time points for liver tumor biopsies
